5.3 Reminder Contacts (Days 5-6, 12-13, 19-20, 26-27, and 33-34)

Contact the participant by telephone, fax, and/or e-mail to remind him of his next scheduled visit, and to bring all required materials to the visit (used and unused product syringes, study diary, concomitant medication bottles, etc).

5.4 Post-Use Evaluation Visits (Days 7, 21, and 35)

- Confirm participant identity and verify Participant ID number.
- Update locator information.
- Collect used and unused product syringes, review the participant's diary and obtain a medical history to assess adherence with all protocol requirements and determine whether any AEs were experienced during the product use period.
- Perform genital exam, including visual inspection of the penile shaft, foreskin, and glans; use hand held lens to examine any observed abnormalities. Take digital photograph of any observed abnormalities, and of normal area(s) if needed for clinical decision-making and/or documentation purposes.
- Collect urine and perform dipstick urine LE test.
- If any AEs are observed/reported, assess the reported events clinically and provide or refer the participant to appropriate medical care; follow and report on all AEs as described in Section 6.
- Administer Acceptability Assessment.
- Schedule next visit (i.e., Day 14 or Day 28 Post-Washout/Pre-Product Use Visit) and provide instructions for washout period (not applicable on Day *35*).
- Complete and submit all required data collection forms.

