2.3 Study Design

This is a Phase I, randomized, blinded, crossover study to be conducted among 24 HIV-infected men residing in the Seattle, WA, area. Half of the 24 participants will be circumcised and half will be uncircumcised. The study design is summarized in the Schema above and the Schedule of Events in Appendix I. Participants will complete three weeks of nightly product application — one week each of BufferGel, PRO 2000/5 Gel (P), and placebo gel — with a one-week washout period between product use periods.

After providing written informed consent, potential study participants will undergo eligibility screening, including medical history, directed physical exam, genital exam, and urine testing. Eligible participants will be assigned at random to one of six possible sequences of product use (e.g., BufferGel followed by placebo gel followed by PRO 2000/5 Gel (P)). Two randomization schedules will be used to ensure balanced assignment among circumcised and uncircumcised men.

Following randomization, participants will be provided with

- seven days worth of the first product in their assigned sequence;
- study diaries on which to record the date and time of product application and removal, as well as any symptoms experienced and/or medications taken; and
- verbal and written instructions for product application and diary completion.

Participants also will receive verbal and written instructions to contact the site to report symptoms and/or discuss any concerns or questions they may have. Throughout the study, interim visits will be conducted as needed to evaluate reported symptoms.

Participants will apply the first assigned product to the penis once nightly. They then will complete a follow-up evaluation on study Day 7. The evaluation will consist of a medical history, review of the participant's study diary, genital exam, and urine testing. Adherence to the product application regimen will be assessed by reviewing participants' study diaries, observing the quantity of used and unused product supplies returned to the study site, and discussing participants' experiences. The occurrence of adverse events during the product use period will be ascertained by reviewing participants' study diaries and obtaining a clinical history since the last visit. Participants will complete a self-administered questionnaire to assess product acceptability.

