7.1.2 Secondary Endpoints

Consistent with the secondary study objective to assess the acceptability of BufferGel and PRO 2000/5 Gel (P) among HIV-infected men, the following secondary endpoints will be assessed:

- AEs other than those listed as primary endpoints judged related to product use.
- Reported positive attributes of the study products.
- Reported negative attributes of the study products.
- Reported willingness to use the study products for sexual intercourse.

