7.6 Data Analysis

Primary data analyses will tabulate the number of observed primary endpoints — listed in Section 7.1.1 — by product and circumcision status.

All participants who enroll in the study will be included in each tabulation. Individual participants will contribute once to the calculation of event rates for each product. Additional safety analyses will tabulate the number and type of AEs experienced during use of each product, overall and by severity and relationship to product. The temporal relationship of product application and AE onset, and the duration of symptoms, also will be evaluated.

Due to the modest study sample size, statistical comparisons across products will not be performed. However, analyses will be performed to assess the number and proportion of participants with subjective or objective findings across products, to determine whether individual participants had similar symptoms and/or exam findings across products.

Additional data analyses will tabulate the number and type of positive and negative product attributes reported by study participants on the Acceptability Assessment completed after use of each product. Also tabulated will be the number and percent of participants who report willingness to use each product for sexual intercourse on the Acceptability Assessment. As above, statistical analyses across products will not be performed, however data will be evaluated to determine whether individual participants' had similar perceptions across products.

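### Section 5.4 lists the acceptability questionnaire after the genital exam, urine test and adverse event assessment, so newly disclosed findings may colour the answers; a stated earlier place would reduce this

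*Protocol*

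**What the plan says.** Protocol Section 5.4 gives nine unnumbered bullets for the visits on Days 7, 21 and 35. After identity and locator checks, staff collect syringes, review the diary and take a history, in part to "determine whether any AEs were experienced during the product use period". Next comes the genital exam, in which they "use hand held lens to examine any observed abnormalities" and photograph what they find. Then: "Collect urine and perform dipstick urine LE test". The sixth bullet reads: "If any AEs are observed/reported, assess the reported events clinically and provide or refer the participant to appropriate medical care". The seventh is "Administer Acceptability Assessment". Scheduling and form submission close the list.

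Section 2.3 describes the same visit and ends with the sentence "Participants will complete a self-administered questionnaire to assess product acceptability". Appendix I also places the acceptability row below the exam and urine row.

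Three of the four secondary endpoints in Section 7.1.2 are participant reports on product acceptability: positive attributes, negative attributes, and "Reported willingness to use the study products for sexual intercourse". Section 7.6 handles them descriptively: "Also tabulated will be the number and percent of participants who report willingness to use each product for sexual intercourse". It plans no statistical analysis across products, but it does ask whether a man's perceptions were similar from one product to the next.

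**The concern.** Acceptability ratings are most useful when they record what it was like to use the gel. Some findings at the post-use visit can be news to the man. Appendix III defines questionable erythema as a subtle change, and a positive dipstick result need not come with symptoms. In the printed order, a man could be examined with a lens, photographed, told of a positive test and referred for care, and then be asked whether he would use the product for intercourse. His answer could then reflect the clinician's finding as well as his own experience.

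Blinding does not prevent this. He need not know which gel he used, only that something was found after using it. If findings are more frequent with one gel, the influence would differ by gel. A plain tabulation of percent willing would carry it without any sign that it is there.

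**Working it through.** **Order of steps.** No figure in the protocol bears on this point, so the check is mainly one of reading.

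| Source | Place of the questionnaire | Is the order stated to be binding? |
|---|---|---|
| Section 5.4 | 7th of 9 bullets: after history (3rd), exam (4th), urine test (5th) and adverse event care (6th) | No; unnumbered |
| Section 2.3 | Last sentence of the description of the evaluation, after exam and urine test | No; no time word |
| Appendix I | Row below exam and urine test | No; a table of procedures |
| Section 5.5 (washout visits) | Not given at these visits | Adverse event assessment is listed before the urine test, the reverse of 5.4 |
| Section 10.1 | Conduct of visits is to be outlined in the procedures manual | Manual not shown |

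Every place that mentions the questionnaire puts it after the exam and urine test. No section puts it earlier, and none says that findings are held back until it is completed. But no section fixes the sequence either, and the differing order in 5.5 shows that the bullets are not a strict running order.

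**What an earlier questionnaire can change.** It can change only the effect of findings first disclosed at that same visit. It cannot change the effect of:

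- findings already discussed at an interim visit (Sections 2.3 and 5.7) or when a product was stopped (Section 4.6, Appendix III);
- findings from an earlier period, which a man still knows when he rates the next gel, since each man uses all three;
- symptoms he has noticed and recorded in his own diary.

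**Size.** Let f be the share of men with a finding first learned at the visit, and d the share of those who change their willingness answer because of it. The shift in percent willing on that gel is f × d if all the changes go the same way, and the number of men is 24 × f × d. The protocol gives neither f nor d, so the values below are assumptions.

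| f | d | Shift (points) | Men of 24 |
|---|---|---|---|
| 5% | 25% | 0.05 × 0.25 = 1.25 | 0.3 |
| 10% | 50% | 0.10 × 0.50 = 5 | 1.2 |
| 30% | 50% | 0.30 × 0.50 = 15 | 3.6 |
| 30% | 100% | 0.30 × 1.00 = 30 | 7.2 |

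One man in 24 is 100/24 = 4.2 points, so a single changed answer is visible in the table of results. The range from 1.25 to 30 points only shows that the size is unknown. Values of f near 30% would also need nearly every finding to be new to the man at that visit, which the protocol gives no reason to expect.

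**The case against.** The strongest reply is that the protocol fixes no order, so there is nothing to correct. The bullets are unnumbered, Section 2.3 reads as a summary by topic, and the manual may already place the form earlier. This stands as far as it goes: that men answer after hearing of findings is a likely consequence of the list, not something the protocol states. Against that, Section 10.3 requires full compliance with the protocol, and the protocol offers staff only this one order.

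Second, Section 7.1.2 places product-related adverse events under the acceptability objective, so the sponsor does not claim that acceptability and toxicity are separate. A rating informed by findings might even be wanted. That is a fair choice, but if it is intended, it should be stated.

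Third, a form that asks about negative attributes, if given on arrival, could prompt symptom reports. Reported symptoms are the first primary endpoint (Section 7.1.1) and are drawn from diary and history. That would move a possible bias from a secondary to a primary endpoint. This objection stands against giving the form first. It does not stand against giving it after diary and history.

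A reader might also infer that a different order would remove the bias at no cost, or that it is worth some 5 to 15 points of willingness. The documents support neither inference. Interim and earlier-period findings stay known whatever the order. The 5 to 15 points come from assuming that 10% to 30% of men have a finding and half change their answer, which counts every finding rather than only those newly disclosed and takes the one-half from no source. The prior studies in men described in Section 1.1 give symptoms that the men themselves reported, so they say nothing about unnoticed findings.

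**Conclusion.** The point holds as a minor improvement. The only order the protocol gives puts the questionnaire after the steps at which findings come to light, and a stated earlier place would keep the ratings closer to the man's own experience of the gel. This rests on two assumptions: that staff follow the list as printed, and that men are told of findings as they arise. Both are plausible, but neither is stated.

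The size is unknown. The effect is confined to three descriptive secondary endpoints. As the plan stands, the primary safety endpoints, the sample size and the safety conclusions are not affected.

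**What to change.** In Section 5.4, move the acceptability bullet to directly after the bullet on syringes, diary and history. Add one sentence: the participant completes the questionnaire himself before the genital exam, the urine test and any discussion of their results. Mirror this in Section 2.3 and make sure the procedures manual agrees. Keeping the form after diary and history protects the symptom reports in the first primary endpoint from prompting.

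The form, the visit and the assessments stay the same, and no clinical rule changes. The cost is a minor change in visit flow, since the form must be finished before the exam begins. The report should still note that ratings may reflect findings known from interim visits or earlier periods.

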5.5 Post-Washout/Pre-Product Use Visits (Days 14 and 28)

- Confirm participant identity and verify Participant ID number.
- Update locator information.
- Obtain medical history since last visit (i.e., since Day 7 or Day 21).

- Perform genital exam, including visual inspection of the penile shaft, foreskin, and glans; use hand held lens to examine any observed abnormalities. Take digital photograph of any observed abnormalities, and of normal area(s) if needed for clinical decision-making and/or documentation purposes.
- If any AEs are observed/reported, assess the reported events clinically and provide or refer the participant to appropriate medical care; follow and report on all AEs as described in Section 6.
- Collect urine and perform dipstick urine LE test.
- Determine eligibility to begin next product use period based on medical history, exam findings, and urine test results.
 - ⇒ If the participant **does not** meet the eligibility criteria, extend washout period and schedule another Post-Washout/Pre-Product Use Visit.
 - \Rightarrow If the participant **does** meet the eligibility criteria, **proceed** with the following:
 - Provide the participant with next assigned product, a study diary, and verbal and written instructions for their use.
 - Instruct the participant to abstain from sexual intercourse, masturbation, and other activities that may cause penile irritation or injury.
 - Reinforce contact information and instructions to contact the study site to ask questions and/or report symptoms.
 - Schedule next visit (i.e., Day 21 or Day 35 Post-Use Evaluation Visit).
 - Complete and submit all required data collection forms.

5.6 Unblinding Contact

After all participants have completed the study, and analyses of study data have been completed, the SDMC will provide the Investigator with information on the product use sequence assigned to each participant. If desired by individual participants, site staff may then contact participants (e.g., by phone, fax, e-mail, in-person visit) to inform them of the product use sequence to which they were assigned.

5.7 Interim Contacts and Visits

Interim contacts and visits may be performed at participant request at any time during the study. All interim contacts and visits must be documented in participants' study records and on applicable case report forms. When interim contacts or visits are conducted in follow-up to participant reports of AEs, study staff will assess the reported event clinically and provide or refer the participant to appropriate medical care; all AEs will be followed and reported as described in Section 6.

6 ADVERSE EVENT REPORTING REQUIREMENTS

Study participants will be provided with 24-hour contact information and instructions to contact the study clinician to report any AEs they may experience, except for life-threatening events, for which they will be instructed to seek immediate emergency care. Study clinicians will instruct participants who report AEs associated with the use of study product to wash off the product with warm water and — depending on the severity of the event — to present to the study site (for more mild events) or to an emergency room (for more serious events) for immediate evaluation. Based on the results of this evaluation, the Investigator will recommend either continuation or discontinuation of product use, consistent with the criteria specified in Appendix III. The Investigator also may prescribe or recommend the use of medications or other preparations to treat the AE.

Where feasible and medically appropriate, participants will be encouraged to seek medical care where the study clinician is based, and to request that the clinician be paged or otherwise contacted upon their arrival. With appropriate permission of the participant, records from all non-study medical providers related to AEs will be obtained and required data elements will be recorded on study case report forms. All participants reporting an AE will be followed clinically, until the AE resolves (returns to baseline) or stabilizes.

Study site staff will document on study case report forms all AEs reported by or observed in enrolled study participants regardless of severity and presumed relationship to study product. All AEs will be defined according to the DAIDS SAE Reporting Manual for the HPTN (dated June 1, 2001). All AEs will be graded using the DAIDS Table for Grading Severity of Adverse Experiences (also referred to as the "Toxicity Table"). Both the DAIDS SAE Reporting Manual and the Toxicity Table are provided in the study-specific procedures manual.

Site staff also will report all AEs that meet serious adverse event (SAE) reporting requirements to the DAIDS Regulatory Operations Center (ROC), according to the procedures and time frames set forth in the DAIDS SAE Reporting Manual for the HPTN. The "intensive" reporting requirements specified in the DAIDS SAE Reporting Manual will be followed. ROC staff will forward SAE reports to the NIAID Medical Officer and the Safety Specialist at the DAIDS Regulatory Affairs Brach. Information on all AEs will be included in reports to the US Food and Drug Administration (FDA) and other applicable regulatory authorities. Site staff also will report information on all AEs and SAEs to their IRB in accordance with Federal regulations and local IRB requirements.

7 STATISTICAL CONSIDERATIONS

7.1 General Design

This is a Phase I, randomized, blinded, crossover study with one week of participant exposure to each of two investigational products — BufferGel and PRO 2000/5 Gel (P) — and a placebo control gel. Each week of exposure will be separated by a minimum one-week washout period. Participants will be assigned at random to one of six possible sequences of product use, balanced within circumcised and uncircumcised participants. Product safety and acceptability will be assessed after application of each product once nightly for a period of seven consecutive nights.

7.1.1 Primary Endpoints

Consistent with the primary study objective to assess the toxicity of BufferGel and PRO 2000/5 Gel (P) on the penile epithelium and urethral mucosa of HIV-infected men, the following primary endpoints will be assessed:

- Participant reports of urethral pain, urethral burning, penile itching, penile rash, or penile ulceration.
- Erythema (with or without induration), vesiculation, bullous reaction, and ulceration, of the penile shaft, foreskin, and glans, as observed by visual exam.
- Erythema or ulceration of the urethral meatus, as observed by visual exam.
- Positive (i.e., greater than trace) urine LE test.

7.1.2 Secondary Endpoints

Consistent with the secondary study objective to assess the acceptability of BufferGel and PRO 2000/5 Gel (P) among HIV-infected men, the following secondary endpoints will be assessed:

- AEs other than those listed as primary endpoints judged related to product use.
- Reported positive attributes of the study products.
- Reported negative attributes of the study products.
- Reported willingness to use the study products for sexual intercourse.

7.2 Sample Size and Accrual

A minimum of 24 "adherent" (as defined in Section 4.5) HIV-infected men — 12 circumcised and 12 uncircumcised — will be included in the study. Based on preliminary estimates, it is expected that 9-12 participants will be enrolled per month, and that 24 participants will be accrued within three months. Additional participants may be included in the study as needed to replace non-adherent participants, as described in Section 4.5.

The table below presents the probability of observing either zero or two or more safety outcomes among groups of 12 (circumcised or uncircumcised) or 24 (circumcised and uncircumcised) participants for various "true" event rates.

	P(0 events observed)		P(2+ events observed)	
Event Rate	n=12	n=24	N=12	n=24
1%	.89	.79	<.01	.02
5%	.54	.29	.12	.34
10%	.28	.08	.34	.71
20%	.07	.005	.73	.97
30%	.01	<.001	.91	>.99
40%	.002	<.001	.98	>.99
50%	<.001	<.001	>.99	>.99

Based on the above, if any safety outcome occurs at a rate of less than five percent, then the probability of observing at least two such events is 12 percent among 12 participants (e.g., the subset of uncircumcised men) and 34 percent among 24 participants. Alternatively, 12 participants provide 91 percent power to exclude event rates of 30 percent or more, and 24 participants provide 97 percent power to exclude event rates of 20 percent or more.

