Particularly in light of the most recent findings with respect to the effects of nonoxynol-9 products, increasing attention has been given to developing non-detergent topical microbicides to prevent HIV infection. Two such products are BufferGel, developed by Reprotect, LLC, and PRO 2000/5 Gel (P), developed by Procept, Inc. and acquired recently by Interneuron Pharmaceuticals, Inc. BufferGel is designed to protect against HIV infection by maintaining the normally acidic pH of the vagina in the presence of ejaculate. PRO 2000/5 Gel (P) is designed to protect against HIV infection by inhibiting viral entry into susceptible cells.

BufferGel and PRO 2000/5 Gel (P) currently are not approved by the US Food and Drug Administration (FDA) for any use. However, both products have undergone extensive pre-clinical testing, both have been shown to inhibit/inactivate HIV in vitro, and both are compatible with condoms. Both products also have undergone clinical testing in Phase I trials among healthy HIV-uninfected sexually abstinent and sexually active women. PRO 2000/5 Gel (P) also has been tested among HIV-infected women. In these studies, the products were shown to be safe and acceptable for vaginal use [10-13].

Phase I trials also have been conducted to assess the safety of BufferGel and PRO 2000/5 Gel (P) on the penile epithelium and urethral mucosa. In one trial, HIV-uninfected men applied either PRO 2000/5 Gel (P) (n=24) or a gel containing the inactive ingredients of PRO 2000/5 Gel (P) (n=12) to the penis for seven consecutive days. About one in three users of the active gel and one in four users of the inactive gel reported mild symptoms of genital itching, tingling, irritation, dryness, discoloration, or flaking of the dried gel. In a similar trial comparing BufferGel and K-Y Jelly (a marketed sexual lubricant), about one in eight users of BufferGel and one in six users of K-Y Jelly reported similar symptoms.

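### Section 7.2 presents the probability of seeing two or more events at a high true rate as power to exclude that rate, and gives the 5 percent values as if they held for every lower rate

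*Protocol*

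**What the plan says.** Section 7.2 fixes a minimum of 24 adherent men, 12 circumcised and 12 uncircumcised. It then describes what those numbers can show: "The table below presents the probability of observing either zero or two or more safety outcomes", for groups of 12 and 24, at true rates from 1 to 50 percent.

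Two sentences interpret the table. The first gives two values, 12 percent for 12 men and 34 percent for 24, for the following: "if any safety outcome occurs at a rate of less than five percent, then the probability of observing at least two such events". The second says that "12 participants provide 91 percent power to exclude event rates of 30 percent or more, and 24 participants provide 97 percent power to exclude"; the limit for the larger group is 20 percent.

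The section gives no confidence level, no count that would amount to exclusion, and no assumed true rate below the limit. Section 7.6 plans tabulation of endpoints by product and circumcision status, without statistical comparison across products.

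**The concern.** Power to exclude a rate is the chance that the observed count is low enough to rule that rate out when the true rate is lower. The 91 and 97 percent figures are calculated with the true rate at the limit itself, and they count the outcomes (two or more events) that would not support exclusion. Read as power, the figure would rise as the product became more toxic: for n=12 the same column goes from .91 at 30 percent to .98 at 40 percent.

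These sentences are the protocol's only statement of what 12 and 24 men can establish. The analysis is descriptive, so a reader faced with a low count will turn to section 7.2 to interpret it. That reader could conclude that a benign product is almost certain to be cleared of a 30 or 20 percent event rate, which the section does not show.

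**Working it through.** **Inputs.** From section 7.2: n=12 and n=24, limits of 30 and 20 percent, stated figures of 91 and 97 percent. The section gives no confidence level; one-sided 95 percent exact (Clopper-Pearson) bounds are assumed in step 3, with 90 and 97.5 percent as variants. True rates of 1, 5 and 10 percent are rows of the protocol's table.

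**1. Reproduce the stated figures.** P(X ≥ 2) = 1 − (1−p)^n − n·p·(1−p)^(n−1).

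- n=12, p=0.30: 1 − 0.0138 − 0.0712 = 0.915 (table .91).
- n=24, p=0.20: 1 − 0.0047 − 0.0283 = 0.967 (table .97).

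The other table cells also reproduce. So 91 and 97 percent are P(2+ events) when the true rate equals the limit. The complements, 8.5 and 3.3 percent, are the chances of 0 or 1 event at that rate. A rule that excludes the limit on 0-1 events therefore has about 91.5 percent (n=12) and 96.7 percent (n=24) confidence.

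**2. Chance of exclusion under the 0-1 event rule.** This is P(X ≤ 1) = 1 − P(X ≥ 2) at the lower true rate, so it follows from the protocol's own P(2+) column.

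| True rate | n=12, limit 30% | n=24, limit 20% |
|---|---|---|
| 1% | 99.4% | 97.6% |
| 5% | 88.2% | 66.1% |
| 10% | 65.9% | 29.2% |

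Under this rule, n=12 reaches 91 percent only if the true rate is about 4.3 percent or less, and n=24 reaches 97 percent only if it is about 1.1 percent or less.

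**3. Chance of exclusion at one-sided 95 percent confidence (assumed).** With 0 events the upper bound is 1 − 0.05^(1/n); for other counts it is the exact beta quantile.

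- n=12: 0 events gives 22.1 percent and 1 event gives 33.9 percent, so excluding 30 percent needs 0 events. The chance is (1−p)^12: 88.6, 54.0 and 28.2 percent at true rates of 1, 5 and 10 percent.
- n=24: 0 events gives 11.7 percent, 1 gives 18.3 percent and 2 give 24.0 percent, so excluding 20 percent allows 0-1 events. The chances are those in the table above.

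Variants at a true 5 percent rate: with a 90 percent bound both groups allow 0-1 events (88.2 and 66.1 percent); with a 97.5 percent bound both need 0 events (54.0 and 29.2 percent).

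**4. The 5 percent sentence.** P(X ≥ 2) at exactly 5 percent is 0.118 (n=12) and 0.339 (n=24), which are the stated 12 and 34 percent. At 1 percent it is 0.006 and 0.024. The probability rises with p, so for rates below 5 percent the stated values are upper limits.

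**The case against.** The strongest reply is that nothing was miscalculated. The table is correct, its P(2+) column stands directly above the sentences, and a reader can see where 91 and 97 percent come from. Read as the confidence of a 0-1 event rule, the figures are meaningful. This stands: the fault is one of label and interpretation. It does not make the word power correct, because confidence and power answer different questions.

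A reader might infer that the true chance of exclusion is always far below the stated figures. The documents do not support that. It depends on a confidence level and a true rate that section 7.2 does not give. At a true 1 percent rate and 95 percent confidence, n=24 gives 97.6 percent, no lower than the stated 97, and n=12 gives 88.6 percent, close to 91. Likewise, 1 event in 12 fails to exclude 30 percent at 95 percent confidence but does exclude it at 90 percent (upper bound 28.75 percent).

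A reader might also turn to section 1.1, where "About one in three users of the active gel and one in four users of the inactive gel reported mild symptoms", and conclude that exclusion is nearly impossible in this trial. Those rates are not a fair planning value. They pool tingling, dryness, discoloration and flaking of dried gel, which are not among the primary endpoints in section 7.1.1, and they come from HIV-uninfected men. Moreover, failing to exclude 20 percent when the truth is about one in three is what a sound design should do.

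Finally, the consequence is limited. Section 7.2 does not derive 24 from these figures, section 7.6 plans no test against the limits, and the accrual-suspension rule in section 7.5 rests on related grade 3 or higher events in at least two men.

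**Conclusion.** The point holds as a mislabelled quantity. The 91 and 97 percent are detection probabilities at true rates of 30 and 20 percent, or equally the confidence of a 0-1 event exclusion rule; they are not power to exclude. How far the chance of exclusion falls below them depends on the unstated true rate. At 1 percent the gap is small or absent. At 5 percent under the 0-1 event rule it is slight for n=12 (88 against 91) and large for n=24 (66 against 97). At 10 percent it is large for both (66 and 29). The n=12 values of 89, 54 and 28 percent rest on the added assumption of one-sided 95 percent confidence.

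The 5 percent sentence is wrong as worded, with no assumption needed. Both sentences should be corrected. The documents do not support calling the table miscalculated or the sample size invalid, and no endpoint, analysis or stopping decision changes.

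**What to change.** Replace the exclusion sentence with: *If the true event rate is 30 percent (20 percent) or more, the probability of observing at least two events is at least 91 percent among 12 (97 percent among 24) participants.*

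In the preceding sentence, state the probabilities as at most 12 percent among 12 participants and at most 34 percent among 24.

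If the protocol also wishes to claim exclusion, add the exact one-sided 95 percent upper bounds by count (0/12: 22.1 percent; 1/12: 33.9 percent; 0/24: 11.7 percent; 1/24: 18.3 percent), and give the assumed true rate and confidence level beside any power figure. This addition is optional; the rewording alone removes the error.

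The cost is wording only: no extra participants, visits or analyses. Any exclusion power then quoted will look less favourable than 91 and 97 percent unless the assumed true rate is very low.
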